1. SYNOPSIS

Table 1: Protocol Synopsis

Title	Central Thalamic Deep Brain Stimulation for the Treatment of Traumatic Brain Injury
Study Groups	Single arm study of 6 subjects
Study Objective	Pilot study to inform the safety and efficacy of central thalamic-deep brain stimulation (CT-DBS) in the treatment of chronic cognitive impairment and residual disability caused by traumatic brain injury (TBI).
Study Device	Medtronic Percept PC system for central thalamic deep brain stimulation (CT-DBS)
Clinical Hypothesis	CT-DBS will be safe in the study population and will enhance cognitive function as indexed by the primary outcome measure
Study Population	Adult patients with a history of moderate to severe TBI (GCS ≤ 12) who continue to demonstrate neuropsychological impairment and functional disability (Glasgow Outcome Scale- Extended = 5-7) at least 24 months post-injury. The 6 participants will be separated into three pairs.
Study Design	Single arm, open-label, sponsor-investigator study
Number of Sites	1 site
Total Number of Subjects	18 subjects screened with a total of 6 subjects enrolled for randomization and implantation
Duration of Study	The total duration of the study is 12 to 14 months depending on cohort.
Inclusion Criteria	
 • History of moderate to severe TBI based on worst GCS score within first 48 hours of injury (acceptable GCS range = 3-12) • Age 22-60 • At least 24 months from date of onset • Fluent in English and able to independently provide consent • Retains decision-making capacity and is able to function independently (i.e., unsupervised) in the home setting • Multiple unsuccessful attempts to sustain competitive employment or complete an academic degree-granting program of study • Either receives no CNS stimulants or other medications known to affect cognitive function, or on stable doses of these medications for the last three months (see additional information regarding concomitant medications below)


Exclusion Criteria
	
 • History of major developmental, neurologic, psychiatric or substance use disorder with evidence of disability prior to onset of TBI • Major medical co-morbidities including: end stage renal failure, severe heart failure, coagulopathy, severe respiratory problems, severe liver failure, uncontrolled hypertension or other significant medical co morbidities • Have had a documented seizure within 3 months of study screening (subjects may re-screen if seizure free after initial screen failure) • Malignancy with < 5 years life expectancy • Untreated / uncontrolled (severe at the time of enrollment) depression or other psychiatric disorder • Women of childbearing age who do not regularly use an accepted contraceptive method • Inability to stop anticoagulation therapy or platelet anti-aggregation therapy before, during and after surgery • Previous DBS or other brain implants • Previous ablative intracranial surgery • Implantable hardware not compatible with MRI • Condition requiring diathermy after DBS implantation • Hardware, lesions or other factors limiting placement of electrodes in optimal target location in the judgment of the operating surgeon • Concurrent enrollment in any other clinical trial • Any condition or finding that, in the judgment of the PI, significantly increases risk or significantly reduces the likelihood of benefit from DBS

Main Study Phases/Activities
	
 • Pre-screening Evaluation and Informed Consent • Randomization to 1of 3 baseline conditions lasting 30, 44 or 58 days. Each participant will also be randomly assigned to a treatment withdrawal or continuation condition for 21 days following the 90-day unblinded treatment phase • Baseline physical and neurological pre-operative examinations • Hospitalization and surgical implantation of DBS system • Post-operative washout (30-day surgical washout for resolution of any transient physiological or behavioral effects of surgery) • DBS Stimulation Titration/Optimization (14 days, optimize settings to be used during treatment phase) • Unblinded Treatment Phase (90 days) • Randomization to treatment withdrawal or continuation • 6-month open label follow up

Outcome Measures
	
Primary outcome measure:
 
 ○ Trail Making test 
Secondary outcome measures include:
 
 • Measures of Cognition 
 ○ Ruff 2 & 7 • Physical Symptoms (self-report)

	
 ○ Rivermead Post-Concussion Symptom Questionnaire (RPQ) ● Psychological Health (Self-report) 
 ○ Patient Health Questionnaire-9 (PHQ-9) ○ Columbia Suicide Severity Rating Scale (C-SSRS) ● Quality of Life 
 ○ Traumatic Brain Injury Quality of Life (TBI-QoL subscales) ● Measure of Global Function 
 ○ Glasgow Outcome Scale – Extended (GOSE)
Safety Endpoints	Rate of adverse events, serious adverse events and adverse device effects
Statistical Methods and Sample Size Determination	This is a single center, feasibility study to be performed by a sponsor investigator at an academic institution. All baseline, procedural, and safety and effectiveness follow-up data will be summarized with appropriate descriptive statistics. For continuous variables, we will summarize data by the mean, median, standard deviation, minimum and maximum. For non-continuous variables we will summarize by percentages and frequency distributions. We will tabulate data for all enrolled patients.

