2. INTRODUCTION

This study involves the treatment of cognitive impairment secondary to traumatic brain injury (TBI) using the Medtronic Percept PC for central thalamic deep brain stimulation (CT-DBS). The proposed study, if successful, will provide supporting evidence for the development of a novel therapeutic approach utilizing CT-DBS to improve these enduring cognitive impairments arising in persons with multi-focal structural brain injuries. This research will address the critical gap of the lack of any available treatments. CT-DBS targets well-defined neuronal populations within the central thalamus that have known anatomical and physiological specializations, which not only provide a key role in arousal regulation during cognitively-mediated behaviors, but also exhibit a particular vulnerability to dysfunction in the setting of multi-focal, non-selective brain injuries.

The proposed study builds on a previous clinical study of CT-DBS in subjects with very severe traumatic brain injuries ([name] et al. 2007 [22]; [name] et al. 2012 [10]). In the preliminary clinical and preclinical studies, we have identified that CT/DBS acts through specific circuit and cellular mechanisms that counter the effects of deafferentation and impaired cellular function across long-range cortico- cortical connections and modulatory cortico-striato-pallidal-thalamocortical pathways following brain injuries by direct activation of the frontostriatal network. We have further identified a strategic location within the three-dimensional confines of the central thalamus that provides an optimal means for facilitating arousal, attention, executive function and motivation.

Our proposed study aims to support development of CT-DBS as a novel therapeutic avenue for accessing cognitive reserve in patients with acquired brain injuries. In the proposed feasibility study of 6 subjects at a single investigational site, we will test the safety of CT-DBS in the moderate to severe traumatic brain injury (SMTBI) population with GOSE 5-7 level recovery and collect data to establish the translation of preclinical studies into human application of CT-DBS. We estimate a screen failure rate of 3:1 for this study.

This is a single-site feasibility study being conducted by a sponsor-investigator. There have been no changes made to the Medtronic Percept PC for use in this study.

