- Treatment will be withdrawn in a double-blinded manner- neither the investigators nor the subjects will have knowledge of when CT-DBS is discontinued. This feature will minimize the influence of examiner and subject bias on the outcomes of interest.
- Outcome assessment across multiple subjects following establishment of a stable baseline will enable identification of a significant treatment effect and permit inferences to be drawn concerning generalizability of results ([name], 2007 [22], Behavioral improvements with thalamic stimulation after severe traumatic brain injury).

Study Operations: This is a single site study. All procedures, assessments and follow-up care will be take place at Stanford University under the leadership of [name]. The study co-investigators from Weill-Cornell, Spaulding Rehabilitation/Harvard, Cleveland Clinic and University of Utah will travel to Stanford for procedures. Two additional Weill-Cornell faculty members will travel to Stanford to do EEG testing and other data collection. [name] at Weill-Cornell will lead the data analysis.

The members of the team have had successful remote collaborations for over a decade. The project has adequate funding for remote collaboration tools for conference calling and document sharing, travel for in-person meetings and a project manager.

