11. STATISTICAL PLAN

This is a feasibility study to inform the safety and efficacy of central thalamic-deep brain stimulation (CT-DBS) in the treatment of chronic cognitive impairment and residual disability caused by traumatic brain injury (TBI). The primary outcome measure used will be the Trail Making test and secondary outcome measures include measures of cognition (Ruff 2 & 7), physical symptoms (Rivermead Post-Concussion Symptom Questionnaire (RPQ)), psychological health (Patient Health Questionnaire-9 and Columbia Suicide Severity Rating Scale (C-SSRS)), quality of life (Traumatic Brain Injury Quality of Life (TBI-QoL subscales)), and measure of global function (Glasgow Outcome Scale-Extended (GOSE)). For the present study all baseline, procedural, and safety and effectiveness follow-up data will be summarized with appropriate descriptive statistics. For continuous variables we will summarize data by the mean, median, standard deviation, minimum and maximum. For non-continuous variables we will summarize by percentages and frequency distributions. We will tabulate data for all enrolled patients. Our statistical analysis will be limited due to the small sample size.

Exploratory statistical analyses of primary and secondary endpoints will be performed to identify potential relationships between the treatment and the outcome variables.

Adverse event data will also be reported and tabulated.

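### The stated claims on safety and generalizability exceed what six participants and a purely descriptive plan can deliver, and the safety rates carry no measure of uncertainty

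*Combined protocol and SAP*

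**What the plan says.** **Claims.** The Clinical Hypothesis row of the synopsis reads "CT-DBS will be safe in the study population and will enhance cognitive function as indexed by the primary outcome measure". The Introduction (Section 2) says, of a feasibility study at one site, "we will test the safety of CT-DBS in the moderate to severe traumatic brain injury (SMTBI) population". Section 6 says that assessing outcomes in several subjects after a stable baseline "will enable identification of a significant treatment effect and permit inferences to be drawn concerning generalizability of results".

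**Design and analysis.** The synopsis describes a "Single arm study of 6 subjects". Its objective row uses milder language than the hypothesis: a pilot meant to inform safety and efficacy. The safety endpoint is "Rate of adverse events, serious adverse events and adverse device effects", without saying whether events or participants are counted. Section 11 says "For non-continuous variables we will summarize by percentages and frequency distributions", gives the usual summary statistics for continuous variables, tabulates adverse events, and mentions exploratory analyses without specifying them. It concedes that the small sample restricts the analysis. Neither the synopsis nor Section 11 names a confidence interval, an acceptable event rate or a criterion for calling the treatment safe.

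**The concern.** A hypothesis with no criterion cannot be confirmed or refuted. The synopsis, Section 2 and Section 6 promise a safety test, a significant effect and generalizable inference, while Section 11 supplies only description. A bare percentage from six people hides how little it rules out.

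At stake is what the final report may say. If no participant, or one, has a serious event, nothing in the plan stops the report from calling the hypothesis supported. Nor does the plan require the reader to be shown that the same data fit high event rates. Pilot safety statements tend to be carried into the rationale for the next study, so the uncertainty should travel with them.

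**Working it through.** **Plan's own figure.** None to reproduce. Six is stated without alpha, power, target rate or margin.

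**Inputs.** n = 6 (synopsis; Section 6). The 95% level and the true risks used below are assumptions, since the documents give neither. All six implanted participants are taken as the denominator; Section 8 says that participants are not replaced after implantation.

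**1. Exact (Clopper-Pearson) two-sided 95% limits.** For x of 6, the lower limit solves P(X ≥ x) = 0.025 and the upper limit solves P(X ≤ x) = 0.025.

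- x = 0: (1 − p)^6 = 0.025, so p = 1 − 0.025^(1/6) = 1 − 0.5407 = 0.459. Interval 0 to 45.9%. The one-sided 95% upper limit is 1 − 0.05^(1/6) = 0.393.
- x = 1: lower limit 1 − 0.975^(1/6) = 0.004. The upper limit solves (1 − p)^6 + 6p(1 − p)^5 = 0.025, giving p = 0.641 (check: 0.0021 + 0.0229 = 0.0250). Interval 0.4 to 64.1%.
- x = 2: 4.3 to 77.7%.

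**2. How often no event would be seen.** P(0 of 6) = (1 − p)^6.

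| True per-participant risk | P(0 of 6) |
|---|---|
| 5% | 73.5% |
| 10% | 53.1% |
| 20% | 26.2% |
| 30% | 11.8% |

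For a 95% chance of seeing at least one event, the true risk must be 1 − 0.05^(1/6), or about 39%.

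**3. Scale.** With zero events, a one-sided 95% upper limit of 10% or less needs n ≥ ln 0.05 / ln 0.90 = 28.4, that is 29 participants. A limit of 5% or less needs 59. These figures show the distance between six participants and a statement about safety; they are not a proposal to enlarge a feasibility study.

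**4. Generalizability.** This rests on reasoning, not on an interval. Six selected participants at one site do not represent the wider population, whatever their results. The staggered baselines of 30, 44 and 58 days do allow one to see whether change follows the onset of stimulation in each participant and recurs across pairs. As an illustration, if all six changed in the same direction, a two-sided sign test would give 2 × (1/2)^6 = 0.031. That supports a limited statement about these six participants, not about patients elsewhere.

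**The case against.** The strongest reply is that the study is plainly labelled as a pilot. The quoted row is a clinical hypothesis, the objective beside it is modest, the Section 2 sentence itself opens by calling this a feasibility study, and Section 11 admits its limits. With six participants, all tabulated, any reader can work out the interval. This stands in part: the fault is a mismatch between sections, not a formal test that lacks power. But the admission in Section 11 neither withdraws the claims nor shows how wide the uncertainty is.

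Stronger readings are tempting and are not supported:

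- *A reader might infer that the plan treats 0 of 6 as proof of safety.* No section contains such a rule. The gap is that safe is undefined, so that report is possible, not prescribed.
- *A reader might take the two-of-six stopping rule in Section 9.5.3 as the only safety criterion.* That rule mandates termination and depends on a sponsor-investigator judgement. Section 10 also has a Clinical Oversight Committee that reviews every serious adverse event as it occurs, meets at least quarterly and may recommend stopping. Section 10.1 adds an independent medical monitor and an ad hoc committee meeting for a serious, study-related unanticipated event. One event can lead to action.
- *A reader might want a binomial interval for participants improved.* The plan defines no responder; the primary measure is a completion time. Such an interval would also not address selection or the single site.
- *A reader might conclude that the design supports no inference at all.* Replication across staggered baselines supports limited inference within the sample.

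**Conclusion.** The point holds as a mismatch between claims and analysis, together with a reporting gap. The synopsis hypothesis, Section 2 and Section 6 go further than six participants at one site and a descriptive plan allow. The safety proportions, as planned, would appear without the information that 0/6 is compatible with a true risk of up to about 45.9%, and 1/6 with up to about 64.1%.

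These sizes assume a two-sided 95% level, independent participants with a common risk, and all six in the denominator. A one-sided 95% limit for 0/6 is 39.3%, which leads to the same conclusion. The point concerns wording and reporting; it does not question the conduct of the trial or its safety oversight.

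**What to change.** 1. **Synopsis hypothesis and Section 2:** reword to match the existing objective, namely to estimate adverse event rates and to describe change in cognition.
2. **Section 6:** limit the generalizability claim to replication of effects across the staggered baselines within these six participants, and bring the wording on a significant effect into line with Section 11.
3. **Section 11:** report the number and proportion of participants with any serious adverse event and with any adverse device effect, each with an exact (Clopper-Pearson) 95% interval. This also settles whether the safety rate counts events or participants. Add a sentence that 0/6 is compatible with a true risk of up to about 45.9% and does not establish safety.

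The sample size and the stopping rule stay as they are.

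**Cost:** wording and a few lines of output; no new data. The stated aim becomes less favourable. Section 13.5 requires FDA and IRB approval for substantive changes, so the rewording may need review. Section 6.6.1 already refers to results from the first five patients, so the change should be dated and recorded as made after most implants. It narrows the claims, so it cannot be seen as favouring the treatment.

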2. INTRODUCTION

This study involves the treatment of cognitive impairment secondary to traumatic brain injury (TBI) using the Medtronic Percept PC for central thalamic deep brain stimulation (CT-DBS). The proposed study, if successful, will provide supporting evidence for the development of a novel therapeutic approach utilizing CT-DBS to improve these enduring cognitive impairments arising in persons with multi-focal structural brain injuries. This research will address the critical gap of the lack of any available treatments. CT-DBS targets well-defined neuronal populations within the central thalamus that have known anatomical and physiological specializations, which not only provide a key role in arousal regulation during cognitively-mediated behaviors, but also exhibit a particular vulnerability to dysfunction in the setting of multi-focal, non-selective brain injuries.

The proposed study builds on a previous clinical study of CT-DBS in subjects with very severe traumatic brain injuries ([name] et al. 2007 [22]; [name] et al. 2012 [10]). In the preliminary clinical and preclinical studies, we have identified that CT/DBS acts through specific circuit and cellular mechanisms that counter the effects of deafferentation and impaired cellular function across long-range cortico- cortical connections and modulatory cortico-striato-pallidal-thalamocortical pathways following brain injuries by direct activation of the frontostriatal network. We have further identified a strategic location within the three-dimensional confines of the central thalamus that provides an optimal means for facilitating arousal, attention, executive function and motivation.

Our proposed study aims to support development of CT-DBS as a novel therapeutic avenue for accessing cognitive reserve in patients with acquired brain injuries. In the proposed feasibility study of 6 subjects at a single investigational site, we will test the safety of CT-DBS in the moderate to severe traumatic brain injury (SMTBI) population with GOSE 5-7 level recovery and collect data to establish the translation of preclinical studies into human application of CT-DBS. We estimate a screen failure rate of 3:1 for this study.

This is a single-site feasibility study being conducted by a sponsor-investigator. There have been no changes made to the Medtronic Percept PC for use in this study.

2.1. Traumatic Brain Injury

TBI is a leading cause of death and long-term disability in the United States as well as worldwide (Murray and Lopez 1997 [19]). Significant attention has been given to TBI in recent years, particularly due to significant numbers of military personnel who have suffered TBI in combat since 2000. According to the Defense and Veterans Brain Injury Center, there were 212,742 TBIs between 2000-2011Q1 in all Armed Forces and 2,235 of these were severe TBIs. Additionally, the statistics of TBI are even more concerning in the civilian population. In addition to 50,000 TBI-related deaths in the US civilian population, there are over 1 million Americans treated in emergency departments every year and 235,000 hospital admissions (Corrigan et al. 2010 [4]). It is estimated that 43% of those discharged from hospital admissions (124,000 patients per year) will develop long-term disability due to TBI (Selassie et al. 2008 [27]). Thus, TBI disproportionately affects young and otherwise healthy individuals who could contribute to the work force. The intervention proposed here is aimed at providing functional improvements that may produce social and vocational reentry and improved vocational performance. Successful treatment of individuals in this disability range thus has the potential for tremendous impact, both for the individual and for society.

Deep brain stimulation is a standard FDA approved treatment for advanced movement disorders and holds great promise for other neurologic disorders, including TBI because of its distinct mechanism of action that can produce control of axonal action potential generation. The safety and feasibility of DBS for patients in chronic post-traumatic injury who fulfilled the behavioral criteria for the minimally conscious state (MCS) and emergence from minimally conscious state (MCS and EMCS) has been demonstrated in a previous IDE and we have provided the proof-of-concept that cognitively-mediated functions can be facilitated in chronic brain injury with DBS directed into the central thalamus ([name] et al. 2007 [22]). The scientific basis for the CT/DBS approach taken here has evolved over a 20-year period of study of the pathophysiology of impaired consciousness in human subjects and the physiological investigations of the role of the central thalamus in forebrain arousal regulation (Purpura and [name] 1997 [20]; [name] and Plum 2000 [21]; Shirvalkar et al. 2006 [28]; [name] et al. 2007 [22]; Smith et al. 2009 [29]; [name] 2008 [23], 2009 [24], 2010 [25], 2012 [26]). These studies are described in more detail in the section that follows.

Approximately 70% of persons who sustain moderate to severe TBI experience chronic cognitive impairments (TBI Model Systems National Data and Statistical Center [31]) that disrupt vocational, social and emotional functioning. This is due, in part, to diffuse axonal injury which results in widespread disconnection across the cerebrum, leading to secondary neuronal death concentrated in the intralaminar nuclei of the central thalamus. After one year, one-third of these individuals remain unemployed and nearly 40% continue to require supervision (TBI Model Systems National Data and Statistical Center [31]). After five years, more than 30% still require some level of supervised care, and 29% report dissatisfaction with life (Corrigan 2014 [5]). Self-report and neuropsychometric findings suggest that slowing in processing speed, mental fatigue and deficient mental control contribute significantly to residual disability following TBI. We have established that CT-DBS can significantly modulate and facilitate performance across a wide range of executive function tasks in the non-human primate (Baker et al. 2011 [1]; 2012 [2]) and in a pilot human study ([name] et al. 2007 [22]), including tasks involving sustained

[figure not shown]
attention, working memory and complex visual pattern recognition. We postulate based on our prior investigation that the effects of CT-DBS are mediated by activation of downregulated frontocentral cortical regions and will produce improvements in processing speed and executive functions as measured by standardized neuropsychometric measures (Trails B, continuous performance tasks) and customized behavioral tasks assaying sustained attention and working memory. We also anticipate that these changes in cognitive efficiency will facilitate improvements in vocational productivity, psychological health and self-reported quality of life.

